## **9 STUDY POPULATION**

### **9.1 Inclusion Criteria**

In order to be eligible to participate in this study, an individual must meet all of the following criteria:

- Southern Chinese male or female  $\geq 18$  years.
- In good general health as evidenced by medical history
- Have the ability to understand the requirements of the study, provide written informed consent, including consent for the use and disclosure of research-related health information, and comply with the study data collection procedures. Provide signed and dated informed consent form

### **9.2 Exclusion Criteria**

An individual who meets any of the following criteria will be excluded from participation in this study:

- Subject with familial hypercholesterolemia (31)
- On regular medication(s) which affect gastrointestinal functions and blood lipids level for the past 3 months, such as, but not limited to:
  - Antibiotics of  $>1$  week duration
  - GI related medications such as antacids
- Having blood lipid lowering medications such as statins, selective cholesterol absorption inhibitors (e.g. ezetimibe), fibrates, niacin, resins, omega-3
- Heavy-smokers (more than 1 pack per day)
- Subject with heavy alcohol intake ( $>40$  g/day for men ;  $>30$  g/day for women) (32), or having history of alcohol abuse within 12 months prior to the study
- Subjects with taste aversion to placebo/intervention soya beverages
- Subject refusing to stop the consumption of plant sterols-enriched products if any during the study (other than the studied product) or having regular consumption of sterols/stanols cholesterol-lowering supplements/functional foods or other related products such as:
  - Sterol/ Stanol - containing margarines, milk, yoghurt drink and soya beverages
  - Sterol / Stanol supplements
  - Fish oils & omega-3 supplements
- Subject receiving systemic treatment or topical treatment likely to interfere with evaluation of the study parameters

- Subject currently involved in a clinical trial or in an exclusion period following participation in another clinical trial
- Pregnancy or lactation
- Having soy allergy
- Being a vegan
- Being an athlete
- Concurrently participating in weight management or dietary program
- On diet pills, such as, but not limited to chitosan and dulcolax
- With history of sitosterolemia
- Having history of hypercholesterolemia, diabetes, thyroid disease, severe kidney diseases, cardiovascular diseases, chronic gastrointestinal disorders, cancers and AIDs
- Having history of malabsorption syndrome arising from diseases such as, but not limited to celiac disease, short bowel syndrome, cystic fibrosis, pancreatitis, diseases of gall-bladder, liver or pancreas, intestinal infection, injury, surgery and radiotherapy
- Taking over-the-counter Chinese medications or supplements with cholesterol/lipidlowering and related claims
- High blood cholesterol at screening [Total cholesterol level  $\geq 6.22$ mmol/L]
- High LDL cholesterol [LDL cholesterol level  $\geq 4.15$ mmol/L]
- High blood triglyceride at screening [TG  $\geq 3.39$ mmol/L]
- Anything that would place the individual at increased risk or preclude the individual's full compliance with or completion of the study.

## **9.3 Subject Withdrawal**

### **9.3.1 Reasons for Withdrawal**

Subjects are free to withdraw from participation in the study at any time upon request. Withdrawal from this study will not affect subjects' ability to receive normal medical care and will not lose any benefits to which they would otherwise be entitled.

An investigator may terminate a study subject's participation in the study if:

- Any clinical adverse event (AE), laboratory abnormality, or other medical condition or situation occurs such that continued participation in the study would not be in the best interest of the subject.
- The subject meets an exclusion criterion (either newly developed or not previously recognized) that precludes further study participation.
- The subject do not follow instructions regarding to the study
- The research investigators or ethic committee(s) stop this research project due to any reasons

For subjects meeting violation of exclusion criteria for baseline laboratory values (i.e. lipid profiling) after randomization, subjects' participation will be continued at the discretion of the investigator.

### **9.3.2 Handling of Subject Withdrawals or Subject Discontinuation of Study Intervention**

Effort will be made to collect the safety and efficacy outcome measures of the withdrawn subjects or subjects who discontinue study intervention by undertaking safety follow-up visit to capture adverse events (AEs), unanticipated problems (UPs), and to collect biological specimens for laboratory evaluations. The participation of the withdrawal visit is entirely voluntary.

Since 25% dropout rate is assumed in the calculation of sample size, no replacement of subjects who withdraw or discontinue early will be made.

#### **9.4 Premature Termination or Suspension of Study**

This study may be suspended or prematurely terminated if there is sufficient reasonable cause. Written notification, documenting the reason for study suspension or termination, will be provided by the suspending or terminating party to the study investigators and regulatory authorities. If the study is prematurely terminated or suspended, the principal investigator will promptly inform the IRB and will provide the reason(s) for the termination or suspension.

Circumstances that may warrant termination include, but are not limited to:

- Determination of unexpected, significant, or unacceptable risk to subjects.
- Insufficient adherence to protocol requirements.
- Data that is not sufficiently complete and/or evaluable.
- Determination of futility.

## **10 GROUP ASSIGNMENT PROCEDURES**

### **10.1 Subject Number**

Prior to study intervention at Day 0 (Screening / Baseline visit), the investigator assigns a uniquely identified subject number to each eligible subject chronologically (e.g. 001, 002, etc). The subject number will not be reused. The actual subject number allocated will be recorded on a subject number allocation log.

### **10.2 Randomization Schemes**

The Data Management and Medical Statistics unit in CTC, HKU, will define randomization specifications and generating the randomization codes, prior to the start of the study.

Block randomization with varying block sizes will be performed separately within each stratum to maintain approximately 1:1 allocations of the two study groups.

Four strata are constructed as follows:

#### **Strata:**

1. Male, aged 18-40 years
2. Male, aged >40 years
3. Female, aged 18-40 years
4. Female, aged >40 years

### **10.3 Group Allocation**

A web-based randomization system will be developed by CTC, HKU to carry out the on-line group allocation.

At Day 0 visit, each subject who fulfils all the eligibility criteria will be given a subject number by the Investigator. The Investigator will prescribe the study intervention according to the subject number by completing a prescription form to the unblinded personnel. Once the unblinded personnel receive the prescription form for the subject number, the unblinded personnel will login the web-based randomization system and randomize the subject using the particular subject number. The information about the group assignment to the subject will be printed out [Group Allocation Sheet] from the system as a source document.

#### **10.4 Masking**

This clinical trial is double-blinded in which neither the subjects nor the investigators know which of the subjects belong to the control group or the investigational group. The product manufacturer will help to ensure the products are packaged, coded and labelled in a manner that will not make reference to group allocation.

The whole process of group allocation, study product preparation and dispensing will only be carried out by the designated personnel with privilege of using the web-based randomization system. The blinding of the trial will be maintained throughout the trial until all data entry and processing are complete and the database has been locked.

#### **10.5 Emergency Unblinding**

Breaking of randomization codes will be performed in a medical emergency where knowledge of the blinded treatment is necessary, for the treatment of a safety event, or requested by the PI. In the event of a code break, the person requesting the code break, subject number, reasons for unblinding, date and time should be documented.

## **11 INVESTIGATIONAL AND CONTROL PRODUCT ADMINISTRATION**

### **11.1 Product Description**

#### ***11.1.1 Acquisition***

The investigational and control products will be supplied by VITASOY International Holdings Ltd.

#### ***11.1.2 Formulation, Packaging, and Labeling***

The investigational product is a plant sterols-enriched soya beverage packed in *cartons* and the control product is the same soya beverage except without plant sterols.

All study products will be labeled with a subject number, bar code, manufacturer, instructions for administration, contact information of study staff, caution statements indicating the product is strictly for subject's use and product storage.

#### ***11.1.3 Product Storage and Stability***

The study products have to be stored in cool (around room temperature) and dry place.

### **11.2 Dosage, Preparation and Administration of Study Products**

Investigational Group: Subjects will orally consume 2g of plant sterols daily as provided by one pack of the soya beverage for 3 consecutive weeks, each pack consumed during the main meal.

Control Group: Subjects will orally consume one pack of the soya beverage except without plant sterols for 3 consecutive weeks, each pack consumed during the main meal.

Subjects will be advised to consume the products immediately once the package is opened and store the products in cool place.

### **11.3 Accountability Procedures for the Study Products**

Study products will be distributed to subjects during their screening and baseline visit (Day 0).

All unused products have to be returned to the study staff in the final visit (Day 21  $\pm$ 5) which will be used as a count of subject's compliance with the study products.

## **12 STUDY SCHEDULE AND PROCEDURE**

### **12.1 Study Visit**

#### ***12.1.1 Screening and Enrollment/Baseline (Visit 1, Day 0)***

- Obtain and document signed informed consent form
- Review medical history to determine eligibility based on inclusion/exclusion criteria
- Review and record medications history to determine eligibility based on inclusion/exclusion criteria
- For eligible subject, perform medical examinations
- For eligible subject, collect detailed demographic information, dietary information, medical history, medication history, alcohol, and tobacco use history
- For eligible subject, collect fasting blood specimen and cardiometabolic risk factors
- Schedule follow-up visit for subject who is eligible and available for the duration of the study
- Provide subject with instructions of the administration of study products
- Provide subject with instructions needed to prepare for follow-up study visit; For instance, return the excess product as a measure of product compliance

#### ***12.1.2 End of Study (Visit 2, Day 21 ± 5)***

- Perform physical examinations
- Record adverse events as reported by subject or observed by investigator
- Record concomitant medications as reported by subject
- Collect fasting blood specimen and cardiometabolic risk factors
- Record subject's compliance with the study product

### **12.1.3 Early Withdrawal**

If subject withdraws early or investigator terminates subject's participation, following evaluations will be offered to the subject:

- Perform physical examinations
- Record adverse events as reported by subject or observed by investigator
- Record concomitant medications as reported by subject
- Collect fasting blood specimen and cardiometabolic risk factors
- Record subject's compliance with the study product

## **12.2 Procedures and Evaluations**

### **12.2.1 Clinical Laboratory Evaluations**

42ml peripheral blood sample will be collected from all subjects. The following laboratory assessments will be assessed at baseline and after the 3-week study period.

Biological specimens will be stored under the subject's consent for any genetic and cell analysis related to risk factors of cardiometabolic disease in the future.

### **12.2.2 Special Assays or Procedures**

#### **Fasting lipid profile**

Blood will be collected into EDTA-coated tubes and the plasma levels of total cholesterol (TC), low density lipoprotein (LDL-C), high density lipoprotein (HDL-C) and triglycerides will be measured automatically by electrophoresis (Architect ci8200 analyzer; Abbott Diagnostics, Wiesbaden, Germany) at the certified Clinical Laboratory.

## 13 STUDY MEASUREMENTS AND VARIABLES

### 13.1 Efficacy Measurements

#### 13.1.1 Primary Endpoint

The **primary endpoint** is the mean serum LDL-C at the end of the week 3 after the consumption of plant sterols fortified soya beverage or control product.

#### 13.1.2 Secondary Endpoints

The **secondary endpoints** include the changes of serum LDL-C, HDL-C, total cholesterol, triglycerides (TAG), serum creatinine, fasting blood glucose, other cardiometabolic risk factors and musculoskeletal-related traits from baseline to week 3.

##### Blood Tests:

- Serum LDL-C, HDL-C, total cholesterol, and triglycerides (TAG)
- Serum creatinine and fasting blood glucose

##### Cardiometabolic risk factors:

- Blood pressure, body temperature, body height and weight, waist and hip circumferences

##### Musculoskeletal-related traits:

- Handgrip strength, peak expiratory flow rate, bio-impedance, gait speed and body balance

### 13.2 Safety Measurements

#### 13.2.1 Adverse Events

An adverse event (AE) is any untoward or unfavorable medical occurrence in a human subject, including any abnormal sign (for example, abnormal physical exam or laboratory finding), symptom, or disease, temporally associated with the subject's participation in the research, whether or not considered related to the subject's participation in the research.

The relationship of each AE to the study product is defined as below:

- **Unrelated:** There is no temporal sequence of the AE onset relative to the administration of study product, and /or there is evidence of other cause such as concurrent medication or illness contributed to the event.

- **Possibly related:** A temporal sequence of the AE onset relative to the administration of trial treatment is not clear, alternative causes are also possible.
- **Probably related:** There is a clear temporal sequence of the AE onset relative to the administration of study product, and potential alternative etiology is not apparent.
- **Definitely related:** There is a clear temporal sequence of the AE onset relative to the administration of study product, and no other possible cause.

The severity of each AE will be assessed as described below:

- **Mild:** The AE is transient and easily tolerated by the subject.
- **Moderate:** The AE causes the subject discomfort and interrupts the subject's usual activities.
- **Severe:** The AE causes considerable interference with the subject's usual activities and may be incapacitating or life threatening.

### 13.3 Demographic Information

Demographic information including age, sex and socioeconomic status will be collected during the baseline visit.

### 13.4 Medical History

Medical history including medical and medications history, alcohol, and tobacco use history will be obtained by interview or from medical records during the screening and baseline visit.

### 13.5 Dietary Information

Structured dietary habit questionnaire will be used to evaluate the dietary habit within one month before the screening and end of study visit.

### 13.6 Study Product Compliance

At the end of the study intervention period, subjects need to return all the excess soya beverage packs for counting the measure of compliance.

The study product compliance is calculated by the following equation:

- Study Product Compliance (%) =  $\frac{\text{Observed Consumption}}{\text{Expected Consumption}} \times 100\%$
- Observed consumption = Pack of soy milk dispensed – Pack of soy milk returned
- Expected consumption =  $\sum$  (Expected daily consumption × Number of treatment days)

### **13.7 Prior/Concomitant Medications**

Complete medications history of prescription and over-the-counter medications within 3 months before the screening and baseline visit will be collected.

Detailed information regarding to subject's concomitant medication records including medication name and total dosage will be collected during the baseline and follow-up visit. Any subject receiving the following medications will be excluded from the study:

- On diet pills, such as chitosan and dulcolax
- Ingestion of over-the-counter Chinese medications or supplements with cholesterol/lipidlowering and related claims
- On medications which affect gastrointestinal functions and blood lipids level for the past 3 months, such as,
  - Antibiotics of >1 week duration
  - GI related medications such as antacids
  - Blood lipid lowering medications such as statins, selective cholesterol absorption inhibitors (e.g. ezetimibe), fibrates, niacin, resins, omega- 3

### **13.8 Protocol Deviations**

A protocol deviation is any noncompliance with the clinical study protocol, Good Clinical Practice, or manual of procedures requirements. The noncompliance may be on the part of the subject, the investigator, or study staff. All deviations from the protocol will be recorded in the study subject source documents.

## **14 STATISTICAL SECTION**

### **14.1 Sample Size Rationale**

The primary endpoint is the mean serum LDL-C at the end of the 3-week treatment period. The sample size calculation is based on ANCOVA with baseline serum LDL-C as independent covariate.

According to a previous study (36), the standard deviation of LDL-C at week 4 is approximately 0.85 mmol/l and the estimated correlation coefficient between the outcomes measured at baseline and week 4 is about 0.7. In addition, a minimum difference of 0.28 mmol/l in LDL-C between the groups is considered clinically important.

By using PASS 12 for the sample size calculation, a power of 0.8 and a 5% of the maximum tolerable false positive rate, 75 subjects per group is required to detect the minimum difference between the mean values of LDL-C.

Considering an attrition rate of 25%, a total of 200 subjects will be recruited.

### **14.2 Data Set Analyzed**

The intention-to-treat (ITT) population is consisted of all the cases that are randomized.

The per-protocol (PP) population includes all eligible subjects who have:

- 80% of study product compliance
- Primary efficacy data collected within the pre-specified allowable visit window
- No protocol violation that is clinically significant.

### **14.3 Handling of Missing or Invalid Data**

No data imputation will be performed to replace missing or invalid data.

### **14.4 Demographics and Baseline Characteristics**

Demographics data and other baseline characteristics including medical history, dietary information, physical examination and prior medication will be summarized by appropriate descriptive statistics.

#### **14.5 Primary Efficacy analysis**

ANCOVA will be carried out to compare the serum LDL-C level at week 3 between the groups. The baseline of the response outcome will be used as a covariate to control for initial group differences. A log transformation will be performed if the normality assumption for the ANCOVA model is violated. And if the normality assumption is still not sustained, non-parametric approach might be performed.

The primary efficacy analysis will be performed on both the ITT and the PP populations.

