## 8 STUDY DESIGN

The study is a 3-week, single-center, double-arm, randomized, double-blind clinical study. Healthy, normocholesterolemic Southern Chinese in Hong Kong will be recruited and screened by the inclusion and exclusion criteria.

Two hundred (200) eligible and consented subjects will be assigned to consume either the investigational or control product by stratified randomization, according to the instructions as follows:

- Investigational Group: Daily consumption of 2g of plant sterols as provided by one pack of the plant sterols-enriched soya beverage for 3 consecutive weeks, each pack consumed during the main meal
- Control Group: Daily consumption of one pack of the soya beverage without plant sterols for 3 consecutive weeks, each pack consumed during the main meal

The randomization will be stratified by both gender (male and female) and age group (18-40 years and >40 years).

Subjects will be invited to attend a baseline visit (Day 0), after which study products will be administered for 21 days. A follow-up assessment (Day 21±5) at the end of the study intervention will be performed for outcome assessment. Clinical data and blood specimen will be obtained by trained personnel in both visits. All blood specimens will be analyzed in a centralized and certified clinical laboratory.

Subjects will be asked to refrain from drinking 2 alcoholic or caffeinated beverages per day and advised to maintain their typical diet and physical activity levels. They will also be asked to report any changes in diet or physical activity and symptoms or changes in health and medications throughout the trial.

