#### **14.6 Secondary Efficacy analyses**

Stratified analysis for the primary endpoint will be performed using the ANCOVA model adjusted for gender and age group. Subjects will be classified to one of the following strata:

1. Male, aged 18-40 years
2. Male, aged >40 years
3. Female, aged 18-40 years
4. Female, aged >40 years

The changes of the following response outcomes from baseline to week 3 will be summarized by descriptive statistics:

- Blood Tests: LDL-C, HDL-C, total cholesterol, TAG, creatinine and fasting glucose.
- Cardiometabolic risk factors: Blood pressure, body temperature, weight, BMI, waist and hip circumferences.
- Musculoskeletal-related traits: Handgrip strength, peak expiratory flow rate, bio-impedance, gait speed and body balance

The secondary efficacy analyses will be performed on the ITT population only.

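### Randomisation is blocked within four sex-by-age strata, but the primary ANCOVA leaves the strata out; making the already planned adjusted ANCOVA primary is a minor improvement that needs no extra data or subjects

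*Combined protocol and SAP*

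**What the plan says.** Section 8 sets the stratification: "The randomization will be stratified by both gender (male and female) and age group (18-40 years and >40 years"). Section 10.2 adds "Block randomization with varying block sizes will be performed separately within each stratum" and lists the four resulting strata.

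Section 14.5, repeated in the synopsis, compares week-3 LDL-C between groups by ANCOVA and names one covariate: "The baseline of the response outcome will be used as a covariate to control for initial group differences". Neither sex nor age group is mentioned. On populations it says "The primary efficacy analysis will be performed on both the ITT and the PP populations". It also allows for a transformed outcome, "A log transformation will be performed if the normality assumption for the ANCOVA model is violated", and for a possible non-parametric analysis after that.

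Sex and age group enter in section 14.6 (and its synopsis copy): "Stratified analysis for the primary endpoint will be performed using the ANCOVA model adjusted for gender and age group". That section closes with "The secondary efficacy analyses will be performed on the ITT population only". Section 14.1 matches the primary model: "The sample size calculation is based on ANCOVA with baseline serum LDL-C as independent covariate".

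Taken together, the stratification factors are in no primary model and in no planned PP analysis.

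**The concern.** Blocking within strata forces the arms to be nearly equal in sex and age group, so those factors contribute almost nothing to the chance difference between arms. A model that omits them still counts their effect on LDL-C as residual noise. If sex or age group predicts week-3 LDL-C beyond what baseline LDL-C already carries, the reported standard error is larger than the true sampling variation of the estimate. The confidence interval is then a little too wide and the true type I error falls below 5%.

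What is at stake is a little precision in the primary estimate that the design has already paid for. The validity of the primary test is not in question.

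**Working it through.** **Inputs from section 14.1:** SD 0.85 mmol/l, baseline to follow-up correlation 0.7, difference 0.28 mmol/l, power 0.80, alpha 5%, 75 per group, attrition 25%. Sidedness is not stated. Two-sided testing reproduces the plan's figure and one-sided does not (59 per group).

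**Reproducing the plan's sample size**

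- Residual SD after baseline = 0.85 × √(1 − 0.7²) = 0.607.
- Normal approximation: 2 × (0.607 × (1.960 + 0.842) / 0.28)² = 73.8, so 74 per group. The noncentral t gives 75, with power 80.1%.
- With 25% attrition: 75 / 0.75 = 100 per group, 200 in total.

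The plan's 75 and 200 are therefore correct for the baseline-only model. With three more model terms for the strata and no explanatory value in them, the noncentral t still gives 75.

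**What the strata could add**

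The documents do not say how much LDL-C variance the strata explain. I assume that stratum effects are equal at both visits and explain a share *s* of the raw variance at each, with *s* = 0, 5, 10 or 20%. Variances below are in units of 0.85² = 0.7225.

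- Baseline-only model, reported residual variance: 1 − 0.7² = 0.51. SE = √(2 × 0.7225 × 0.51 / 75) = 0.0991.
- Variance that drives the estimate when strata are balanced, i.e. the within-stratum variance of (week 3 − 0.7 × baseline): 1.49(1 − s) − 1.4(0.7 − s) = 0.51 − 0.09s. SE overstatement = √(0.51 / (0.51 − 0.09s)) − 1.
- Model with strata, residual variance: (1 − s) − (0.7 − s)² / (1 − s). For *s* = 20% this is 0.8 − 0.25/0.8 = 0.4875.
- Type I error and power come from central and noncentral t, with 147 df without and 144 df with the four-level stratum, at 75 completers per arm.

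| Raw share s | Residual variance with strata | Share of post-baseline variance | SE with strata | SE overstated without strata | Type I error without strata | Power without v with strata | CI half-width with strata |
|---|---|---|---|---|---|---|---|
| 0% | 0.510 | 0% | 0.0991 | 0% | 5.0% | 80.13 v 80.12% | 0.196 |
| 5% | 0.505 | 0.9% | 0.0987 | 0.4% | 4.9% | 80.23 v 80.48% | 0.195 |
| 10% | 0.500 | 2.0% | 0.0981 | 0.9% | 4.8% | 80.34 v 80.89% | 0.194 |
| 20% | 0.4875 | 4.4% | 0.0969 | 1.8% | 4.6% | 80.55 v 81.85% | 0.192 |

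The half-width without strata is 0.196 mmol/l throughout. In subjects, the narrower interval is worth 75 × 0.51/0.505 − 75 ≈ 0.7 completers per arm at 5%, and about 1.5 and 3.5 at 10% and 20%.

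**Check by simulation:** 200,000 trials per cell, 150 completers, strata of 38, 38, 38 and 36 (an assumption), Monte Carlo error 0.09 point. Power without v with strata was 79.7 v 79.7, 80.0 v 80.2, 80.0 v 80.6 and 80.4 v 81.7% at *s* = 0, 5, 10 and 20%. Type I error without strata was 5.1, 4.9, 4.9 and 4.6%. The levels sit 0.2 to 0.4 point below the formula for both models, mostly because the formula ignores chance baseline imbalance. Multiplying the variance by 1 + 1/(df − 1) gives 79.9% without and 79.8% with strata at *s* = 0. The gains agree: 0, 0.2, 0.6 and 1.3 points.

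**A different assumption:** if the strata explained 5 or 10% of the variance *left after baseline*, power with strata would be 82.1 or 84.1%. That is a much stronger premise than the same percentages of raw variance, and nothing in the documents supports it.

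**The case against.** The strongest reply is that nothing is broken. The primary model is the one the sample size was built for, and it is valid. The adjusted ANCOVA is already specified on ITT, so an ITT reader sees both estimates under either plan and only the labels change. The gain rests on an assumed share, is at most 1.3 points of power over the range tabulated, and could be zero. Changing a primary analysis also needs ethics approval before it takes effect (section 17.2).

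Most of this stands, and it is why the point is minor. It does not remove the point, because a secondary analysis does not supply the primary estimate, interval or p-value, and it leaves PP without any adjusted result.

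Two cautions on the remedy are also fair. Section 14.6 calls its analysis stratified and sorts subjects into four strata, yet describes an adjusted model. It could mean one pooled model, separate within-stratum estimates, or both, so moving it must not delete a planned output. And the possible non-parametric analysis in section 14.5 might still omit the strata. The change proposed here does not settle that, but makes it no worse.

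**Conclusion.** The point holds as a minor, optional improvement. The trial is stratified by sex and age group and the primary ANCOVA ignores both, although the adjusted model is already written into the plan. Leaving the strata out makes the primary test at most slightly conservative: type I error between 4.6 and 5.0%, and a standard error overstated by 0 to 1.8%.

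These sizes assume stratum effects equal at both visits, 75 completers per arm, arms balanced within strata, and the plan's own SD and correlation. The share explained by the strata is the one input the documents cannot supply, which is why the range includes zero.

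**What to change.** **Section 14.5 and its synopsis copy.** Replace the covariate sentence with text such as: *The primary model, for the ITT and PP populations alike, is an ANCOVA of week-3 LDL-C on treatment, baseline LDL-C and the four-level randomisation stratum of section 10.2. The same terms are kept if LDL-C is log-transformed.*

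**Section 14.6 and its synopsis copy.** Take out the sex- and age-adjusted ANCOVA as a separate secondary analysis and add: *As a sensitivity analysis on ITT, the ANCOVA is repeated with treatment and baseline LDL-C only.* First settle whether per-stratum estimates were also intended; if so, list them separately as subgroup results.

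**Section 14.1 and its synopsis copy (optional).** Note that 75 per group was calculated for the baseline-only model and that the same formula still gives 75 with the stratum term added. A flat promise of at least 80% power is better avoided, because allowing for chance baseline imbalance gives 79.8% when the strata are uninformative.

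**Cost.** Short edits in three sections and their synopsis copies, plus the ethics review that any amendment needs, all before unblinding. Statistically it costs three of 147 degrees of freedom, about 0.01 point of power. No new data are needed, because sex and age group are already recorded to randomise, and the sample size does not change.
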